1.0 Objectives / Specific Aims

Specific Aim 1: Determine the efficacy of motor control deficit guided personalized training on SSWS compared to non-personalized and control interventions. Hypothesis: Individuals receiving walking rehabilitation personalized to their baseline motor control deficit (INCLINE for low Pp and DECLINE for high Pp) will exhibit significantly improved SSWS compared to those receiving non-personalized and control interventions.

Specific Aim 2: Determine the efficacy of motor control deficit guided personalized training on increasing symmetry of Pp compared to non-personalized and control interventions. Hypothesis: Individuals receiving walking rehabilitation personalized to their baseline motor control deficit will exhibit significantly improved symmetry of Pp compared to those receiving non-personalized and control interventions.

Specific Aim 3: Determine if the personalized intervention increase the positive response rate compared to non-personalized and control interventions, and to further advance personalized interventions by identifying factors that predict response. Hypothesis 3.1: A higher percentage of individuals receiving personalized interventions will “respond” than those receiving non-personalized and control interventions. Hypothesis 3.2: Discreet sets of clinical and biomechanical variables will predict responses in those with differing baseline motor control deficits.

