Predicting Responders to a Novel Locomotor Rehabilitation Intervention: Many types of locomotor rehabilitation techniques (activity-based therapies,³⁶ lower extremity strengthening,³⁷ aerobic conditioning,³⁸ functional electrical stimulation³⁹) produce robust changes in functional outcomes such as increased self-selected walking speed (SSWS). However, no single intervention is shown to be superior in producing these functional changes.⁴⁰ In addition, a critical need exists to be able to understand mechanisms associated with recovered function in order to predict responders from non-responders prior to a therapeutic intervention. Currently, mechanistic outcomes are too inconsistently applied to locomotor rehabilitation interventions to draw clear conclusions as to how recovery is generated.^{41,42} Recent analyses have begun to examine the patterns of response in rehabilitation participants in an effort to delineate which participants respond to an intervention and how they improve.⁴³⁻⁴⁵ These analyses, however, typically lack a thorough outcome battery that includes broad-based biomechanical and clinical outcome measures. We believe that a full battery of biomechanical and clinical variables will prove crucial for determining a broader set of factors contributing to response to rehabilitation interventions that clinicians can apply to improve decision making regarding intervention selection. This proposal is guided by the overall hypothesis that when provided an intervention tailored to the baseline motor control deficit, there will be fewer non-responders leading to more robust functional effects.

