low-pass filtered with a fourth-order, zero-lag digital Butterworth filter. To optimize capture of steady state data on the treadmill, subjects will walk for approximately 10 seconds to achieve steady state prior to the 30 seconds of data collection (40 seconds per trial). Two trials will be collected at the treadmill self-selected speed and two trials at the fastest comfortable speed. Biomechanical data collections will allow for secondary analyses of associated kinematic and kinetic variables (e.g. force impulse, COMa by gait cycle phase, joint moments/power/work, and joint angles). At baseline testing, post-testing, and at the beginning of *each session*, participants will walk on a 16 ft. long gait mat (GAITRite) to measure SSWS and fastest comfortable walking speed (FCWS) and other spatiotemporal parameters. Subjects will be permitted a practice trial, and then be asked to complete two trials at each speed. A safety harness mounted to the ceiling will protect the subject but will only support their body weight in the case of a loss of balance. Trained study personnel will be present for all testing sessions as needed.

Clinical Assessments: The proposed assessments are standard to most post-stroke intervention trials. As the primary aim of this proposal is to improve functional outcomes using an intervention that is clinically translatable, it is imperative to include assessments routine to clinical rehabilitation. The below measures reflect a battery of body structure and function, activity, and participation measurement to reflect a broad range of clinical assessment across the rehabilitation model (ICF) as has been previously advocated.⁵⁰ All clinical assessments will be conducted by a physical therapist evaluator blinded to group allocation (different than the training physical therapist) within the Center for Rehabilitation Research in Neurological Conditions.

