Sample Size Determination and Statistical Approach: A total of 72 individuals post-stroke will be recruited for this study. We are assuming an attrition rate of 20% resulting in a final sample size of 60 for statistical analyses, ideally 10 in each combination of baseline group (low and high Pp) and intervention (INCLINE, DECLINE, and CONTROL training). 10% is consistent with attrition rates from previous trials of locomotor rehabilitation conducted by our group,⁴³ but we have chosen a more conservative rate of 20% based on the novelty and intensity of the intervention. There will be two strata of 30 individuals each with baseline low Pp and high Pp, respectively. From those strata, using block randomization, the subjects will be equally randomized into the INCLINE, DECLINE, and CONTROL training (10 in each training cell). The power analysis was based on our pilot training data for INCLINE and DECLINE combined compared to CONTROL. For the power analysis, we used a repeated measures model with an AR(1) correlation value of 0.45 which we obtained from the pilot data. With an average standard deviation of 0.35 (also obtained from the pilot data) and 80% power, with 10 subjects per group we will be able to detect a difference of at least 0.20 between the intervention groups and CONTROL group. A log transformation was applied to achieve normality. Also, we will longitudinally evaluate speed at each session. We will therefore conduct a repeated measures 2-way ANOVA and test the relevant hypotheses using contrasts in a Bonferroni post-hoc analysis. We will include an adjustment for baseline Pp group, intervention group, time, and their interactions. Depending on the within subject correlation across time (which we anticipate to be high) this could also provide additional power. Therefore, in a secondary analysis we will be able to examine several covariates, including the sub-types mentioned above. For each Aim, each variable will be assessed utilizing a repeated measures analysis of variance (baseline Pp, group and time) to evaluate the interaction between baseline Pp, group and time as well as the main effects of treatment for each group and group assignment at each time point. Since pilot data required a log transformation of SSWS, we will assess the final SSWS outcome for normality and perform a transformation if necessary. All power estimates were conducted by a biostatistician ([name]) using PASS 2008 (NCSS, Kaysville, Utah). Spaghetti plots and descriptive statistics regarding HR, BP, and RPE responses to INCLINE and DECLINE training will be reported prior to formal analyses. Patterns of attrition between the 2 groups will also be compared.

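### Hypothesis 3.2 has no analysis that can answer it: the stated ANOVA contains no predictor terms, and unplanned screening in strata of about 30 would be likely to yield chance predictors

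*Combined protocol and SAP*

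**What the plan says.** Section 1.0 states Hypothesis 3.2 without qualification: "Discreet sets of clinical and biomechanical variables will predict responses in those with differing baseline motor control deficits". Section 2.0, under the heading on predicting responders, draws the candidates from the whole assessment set: "a full battery of biomechanical and clinical variables will prove crucial for determining a broader set of factors contributing to response". It adds that clinicians should be able to use these factors when choosing an intervention. Section 4.0 leaves the biomechanical list open: "Biomechanical data collections will allow for secondary analyses of associated kinematic and kinetic variables (e.g. force impulse, COMa by gait cycle phase".

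For the analysis, section 11.0 says: "For each Aim, each variable will be assessed utilizing a repeated measures analysis of variance". The sentence goes on to name baseline Pp, group and time as the factors, with their interaction and main effects as what is assessed. Bonferroni correction is attached to the post-hoc contrasts. The section also allows a secondary look at several covariates, which it does not list.

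On sample size, the same section says: "There will be two strata of 30 individuals each with baseline low Pp and high Pp, respectively", and "the subjects will be equally randomized into the INCLINE, DECLINE, and CONTROL training (10 in each training cell".

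The documents give no candidate list for 3.2, no prediction model, no selection rule or limit on the number of predictors, and no validation. Response has no operational definition either. Section 4.0 cites a minimal clinically important difference of 0.16 m/s for SSWS but does not make it the response criterion.

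**The concern.** The hypothesis and the method do not meet. Hypothesis 3.2 asks which baseline variables predict who responds. The ANOVA asks how each measured variable changes over time by arm and Pp group. Followed exactly, it returns no predictor of response.

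Something else will therefore have to be done once the data are in, and nothing in the plan limits it. The obvious choice is to compare responders with non-responders one variable at a time within each stratum. With about 30 people, an open-ended battery and no correction or validation, that search readily produces predictors by chance.

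There is also a question of meaning. Each stratum mixes three trainings. A variable associated with improvement across all three marks people who improve anyway. To show who benefits from a particular slope, the model needs predictor-by-arm terms. The stated interactions involve only baseline Pp group, intervention group and time.

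Section 2.0 wants the predictors to guide the choice of training, and section 10.0 aims at a clinical decision-making framework. A spurious set could be carried into that use.

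**Working it through.** **1. The plan's own figure.** The only power statement is 80% power for a difference of 0.20 with 10 per group, SD 0.35 and AR(1) correlation 0.45. It concerns intervention against CONTROL. The SD of a mean of m repeated measures is 0.35 × √{[m + 2Σ(m−k)0.45^k]/m²}, summing k from 1 to m−1. With m = 12 (one per session, assumed) the factor is 0.199, so the SD is 0.35 × √0.199 = 0.156. At two-sided alpha 0.05 (assumed; the plan gives none), 10 per group then has 81.7% power and a detectable difference of 0.196. The figure can be reproduced on that reading, but it says nothing about 3.2, which has no sample-size basis.

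**2. What the stated model can estimate.** Outcome: each variable in turn. Factors: baseline Pp group, arm, time. The one baseline characteristic in the model is Pp group, which 3.2 takes as given when it asks for predictors by baseline deficit. No coefficient links a candidate predictor to response.

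**3. People available.** 30 per stratum, 10 per cell. This is slightly generous: "We are assuming an attrition rate of 20% resulting in a final sample size of 60 for statistical analyses", yet 72 × 0.80 = 57.6, or about 29 per stratum.

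**4. Candidates.** The number is not stated. The clinical measures named in section 4.0 (SSWS, fastest comfortable speed, 6MWT, FGA, three Fugl-Meyer scores, SIS, ABC) make 9 with SIS as one score, or 9 − 1 + 9 = 17 with its nine domains. Biomechanics come on top. Assumed range: 10 to 40.

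**5. Chance of a false predictor.** If p candidates are all null and independent, P(at least one p<0.05) = 1 − 0.95^p. For p = 20 this is 1 − 0.95^20 = 0.642, with 20 × 0.05 = 1.0 false predictor expected per stratum. Over both strata it is 1 − 0.95^40 = 0.871.

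**6. Simulation for correlated candidates.** Pure-noise predictors, n = 30, 40% responders (12 people, so 12/20 = 0.6 responders per candidate at p = 20), t-test screening at 0.05, the best three combined linearly, 1,000 datasets per setting. Entries are for inter-predictor correlation 0 / 0.3 / 0.6.

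| Candidates | Formula (independent) | At least one p<0.05 | Apparent AUC of best three |
|---|---|---|---|
| 10 | 40% | 41% / 36% / 26% | 0.773 / 0.754 / 0.717 |
| 20 | 64% | 65% / 55% / 35% | 0.817 / 0.791 / 0.743 |
| 30 | 79% | 78% / 68% / 43% | 0.840 / 0.810 / 0.755 |
| 40 | 87% | 86% / 77% / 52% | 0.857 / 0.822 / 0.767 |

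In new data the AUC was 0.50 throughout. Simulation error on the percentages is at most about √(0.25/1000) = 1.6 points.

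**7. Sensitivity.** With 20 candidates at correlation 0.3, 30% responders gives 55% and AUC 0.81; 50% responders gives 56% and 0.78. With 50% responders and independent candidates the figures are 64% and 0.81. Searching inside one arm of one stratum (n = 10) gives apparent AUCs of 0.88 to 0.99 from noise.

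**8. What a short list achieves.** With two pre-specified candidates at correlation 0.3, the chance of a false predictor falls to 10% and the apparent AUC to 0.64. The true value is still 0.50, so optimism correction remains necessary.

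**The case against.** The strongest objection is that the simulated procedure is not the trial's. T-test screening, a best-three rule and an in-sample AUC appear nowhere in the documents. That stands: the figures illustrate one likely way of filling the gap and do not describe the plan.

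A reader might infer that the plan's ANOVA is itself an unpenalised screen of predictors. The documents do not support this, because each variable is the outcome there. A reader might also infer that the trial would report a predictor set even if nothing predicts response. That too goes beyond the text: nothing is planned in that detail, and under screening between 13% and 74% of null strata (100 − 87 and 100 − 26) would show no variable at p<0.05.

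The size of the illustration can also be challenged. Clinical gait measures overlap; section 4.0 cites correlations of 0.75 and −0.61 between the 6MWT and other mobility measures. Correlation lowers the false-positive rate, which is why ranges are given. With 20 independent null candidates, three or more reach p<0.05 in only 1 − 0.358 − 0.377 − 0.189 = 7.5% of strata, so the best three usually include non-significant variables. Three noise variables fixed in advance already show an apparent AUC of 0.67, so not all of the optimism comes from screening.

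Finally, the plan can be read as partly exploratory: it claims no power for 3.2, calls the kinematic and kinetic work secondary, and mentions a covariate analysis. This softens any charge that 3.2 is firmly confirmatory. However, 3.2 carries no such label, and the covariate sentence neither refers to it nor names a covariate. The absence of a usable method is untouched by any of this.

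**Conclusion.** The concern holds as a gap between hypothesis and method. The analysis stated for every Aim cannot identify predictors of response or distinguish general improvement from benefit of a particular training. This rests on the text alone and needs no assumption.

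The size of the risk is conditional. If the gap is filled by uncorrected screening within strata, the chance of at least one false predictor per stratum runs from about 26% (10 candidates, correlation 0.6) to about 87% (40 independent candidates). At 20 candidates it is about 35% to 64%, with an apparent AUC of about 0.74 to 0.82 for a useless three-variable set. These figures assume 30 people per stratum, alpha 0.05 and 40% to 50% responders; the plan does not state the candidate number, their correlation, the response rate or alpha. Aims 1 and 2 are not affected. The plan should be changed, because 3.2 cannot be interpreted as written.

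**What to change.** In section 11.0, replace the ANOVA for Hypothesis 3.2 with a single shrinkage (penalised) regression on all randomised participants:

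- **Outcome:** change in SSWS at a named time point, transformed if needed, adjusted for baseline SSWS.
- **Terms:** arm, Pp stratum, a short pre-listed set of baseline predictors, and predictor-by-arm and predictor-by-stratum terms. The stratum terms are needed because 3.2 asks for predictors by baseline deficit.
- **Reporting:** bootstrap- or cross-validated performance only, with 3.2 labelled hypothesis-generating.
- **Statement of the change:** say that 3.2 uses continuous change in place of a responder category, while 3.1 keeps its responder comparison.

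The list must be short. Each predictor costs 1 main effect + 2 arm terms + 1 stratum term = 4 coefficients, so five predictors already use 20 with about 60 people.

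The cost is SAP wording and modest extra analysis, with no added participants, visits or measurements. Reported performance will look less favourable, and interaction estimates will be imprecise at about 60 participants.

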- **Walking Speed:** We will assess SSWS and fastest comfortable walking speed in meters per second over a 16 foot GAITRite walkway. Mean SSWS for individuals post-stroke has been established at 0.84m/s,⁵¹ with excellent test-retest reliability (ICC=0.95 to 0.99) and interrater/intrarater reliability (0.87 to 0.88).^{3,52} Minimally Clinically Important Difference (MCID) for SSWS for stroke survivors of 0.16 m/s⁵³ allows for the clinician to set meaningful walking speed goals, while providing a classification for researchers via cut off scores: <0.4 m/s representing likely limited household ambulators, 0.4-0.8 as limited community ambulatory profile, and >0.8 m/s as community ambulators.³
- **6-Minute Walk Test (6MWT):** Timed walking tests are primarily a measure of functional capacity.⁵⁴ The 6MWT tests populations who present with little functional walking capacity and is validated against the Rivermead Mobility Index ($r=0.75$) and 10-meter walk time ($r=-0.61$).⁵⁵ The 6MWT has a high intra- and interrater reliability (ICCs = 0.82-0.95).⁵⁶ The Minimal Detectable Change (MDC) for individuals with chronic stroke is 120 feet⁵⁷ and the MCID is 113 feet.⁵⁸
- **Functional Gait Assessment (FGA):** The FGA is modified from the Dynamic Gait Index and includes 10 items to assess dynamic balance stability during gait. Each item is scored on a 4-point scale from 0 (poor) to 3 (excellent) with a maximum score of 30. The MDC is 4.2 points,⁵⁹ A score 22 or below out of 30 is predictive of falls in older adults (sensitivity and specificity each 85%).⁶⁰
- **Fugl-Meyer Assessment of Motor Function:** We will utilize the lower extremity (LE FM Assessment) portion of the assessment to characterize our participant sample. The LE FM Assessment is a measure of motor recovery post-stroke and includes measures of reflex, motor control, and coordination with a total score of 34. We will also evaluate separately the 22-point motor sub-score as well as the LE sensory portion.⁶¹

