6.0 Number of Subjects

Sample Size Determination and Statistical Approach: A total of 72 individuals post-stroke will be recruited for this study. We are assuming an attrition rate of 20% resulting in a final sample size of 60 for statistical analyses, ideally 10 in each combination of baseline group (low and high Pp) and intervention (INCLINE, DECLINE, and CONTROL training). 10% is consistent with attrition rates from previous trials of locomotor rehabilitation conducted by our group,⁴³ but we have chosen a more conservative rate of 20% based on the novelty and intensity of the intervention. There will be two strata of 30 individuals each with baseline low Pp and high Pp, respectively. From those strata, using block randomization, the subjects will be equally randomized into the INCLINE, DECLINE, and CONTROL training (10 in each training cell).

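### Hypothesis 3.2 reads as a search for predictors of a yes/no response within strata of 30, with no model stated; modelling the size of the change would keep power that a split gives away

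*Combined protocol and SAP*

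**What the plan says.** Section 1.0 gives Aim 3 two hypotheses. Hypothesis 3.1 is about a proportion: "A higher percentage of individuals receiving personalized interventions will “respond” than those receiving non-personalized and control interventions". Hypothesis 3.2 is about prediction by baseline deficit: "Discreet sets of clinical and biomechanical variables will predict responses in those with differing baseline motor control deficits". The Background (section 2.0), under its heading on predicting responders, says mechanisms need to be understood "in order to predict responders from non-responders prior to a therapeutic intervention".

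The outcomes are not binary. Section 4.0 states: "We will assess SSWS and fastest comfortable walking speed in meters per second". It also lists the 6-minute walk, the Functional Gait Assessment (a sum score up to 30) and the absolute deviation of Pp from 0.5. Section 10.0 schedules clinical and biomechanical measures before training, after training and at one month.

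On numbers, section 6.0 states: "There will be two strata of 30 individuals each with baseline low Pp and high Pp, respectively". On analysis, section 11.0 states: "For each Aim, each variable will be assessed utilizing a repeated measures analysis of variance", with baseline Pp, group and time as the factors. It also allows covariates in a secondary analysis. No section defines a response, gives an expected response rate, names the candidate predictors, specifies a model for Hypothesis 3.2 or gives power for Aim 3.

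**The concern.** Scoring each person as responder or non-responder discards how much that person changed. A gain just over the cut counts the same as a large one, and a near miss counts the same as no change. This happens at any cut-off and with any binary method, so defining the cut-off would not recover the information.

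The loss matters most for Hypothesis 3.2. It is examined separately by baseline deficit, with 30 people per stratum spread over three training arms. Its stated purpose is to help clinicians choose an intervention. With so few people, a real predictor of gain could be missed more often than the collected data require. The repeated measures ANOVA in section 11.0 does not fill the gap: it compares groups over time and does not relate a person's change to candidate predictors. The documents cite no guideline that requires a split.

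**Working it through.** **The plan's own figure.** Section 11.0 claims 80% power to detect 0.20 with SD 0.35, AR(1) correlation 0.45 and 10 per group. The number of occasions and alpha are not stated; two-sided 5% is assumed. The SD of a mean over M occasions is 0.35 × √(mean of the AR(1) matrix).
- M = 12, 10 v 10: 0.35 × √0.199 = 0.156; SE = 0.156 × √(2/10) = 0.0698; power = Φ(0.20/0.0698 − 1.96) = 81.7%.
- M = 3, 40 v 20 (sloped arms combined v CONTROL): SD 0.266, SE 0.0729, power 78.3%.
- M = 1, 10 v 10: 24.8%.

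The 80% can be reproduced, but only for some choices of M. It concerns group differences and does not bear on Hypothesis 3.2.

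**Inputs for Hypothesis 3.2.** n = 30 per stratum (section 6.0). Assumed, because the plan is silent: correlation r between one normal predictor and change; responder share p; alpha two-sided 5%.

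**Formulas.** Power on the full scale = Φ(atanh(r) × √(n − 3) − 1.96). Splitting the outcome multiplies r by φ(z_p)/√(p(1 − p)), where z_p is the normal cut-point that leaves share p above it. The factor is 0.3989/0.5 = 0.798 at p = 50%, 0.759 at 30% and 0.700 at 20%.

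**Worked case.** r = 0.5, p = 30%. Full scale: 0.549 × 5.196 − 1.96 = 0.894, power 81.4%. Split: r becomes 0.379; 0.399 × 5.196 − 1.96 = 0.115, power 54.6%. Loss 26.9 points (from unrounded values).

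| r | Full-scale power | Split, 50% respond | Split, 30% respond | Loss (points) |
|---|---|---|---|---|
| 0.3 | 36.3% | 24.5% | 22.5% | 11.8 to 13.8 |
| 0.4 | 59.5% | 40.5% | 37.0% | 19.1 to 22.5 |
| 0.5 | 81.4% | 59.3% | 54.6% | 22.2 to 26.9 |
| 0.6 | 95.0% | 77.3% | 72.3% | 17.7 to 22.6 |

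**Checks.**
- Simulated correlation tests (40,000 runs per case) give 37% v 23–25% at r = 0.3, 83% v 56–62% at r = 0.5, and 95–96% v 75–81% at r = 0.6. The losses run from 12.1 to 26.2 points.
- A logistic likelihood-ratio test on the split outcome loses 10.5 to 23.5 points over the same r and p.
- If 20% of the 72 recruited drop out, 72 × 0.80 = 57.6 remain, about 29 per stratum. For r of 0.3 to 0.5 the formula then gives a loss of 11.4 to 26.9 points.
- Wider inputs at n = 30: simulation gives 5.4 points at r = 0.7 with 50% responding, and 34.3 at r = 0.5 with 20% responding (33.9 by formula).

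**The case against.** The strongest objection is that the plan never states a split for Hypothesis 3.2. Its wording says only that variables predict responses. The responder/non-responder phrase comes from background text about a need in the field. The one analysis named for every Aim uses a quantitative scale. On this view the real defect is that response and the Hypothesis 3.2 analysis are undefined, and the power loss is charged to an analysis nobody has specified. Part of this stands: the yes/no reading of Hypothesis 3.2 is inferred, and a reader should not conclude that the plan commits to it. But Aim 3 as a whole is built on a response rate and on factors that predict response, and the ANOVA is not a predictor analysis. If the sponsor already intends a continuous outcome, the fix only writes that down.

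The size is also open to challenge. r, the responder share and alpha are all assumed. The calculation has one predictor and ignores training arm, whereas Hypothesis 3.2 looks for sets of variables; a search over many would lower both powers. This stands, so no single range can be read as a property of the trial.

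A reader might also infer that Hypothesis 3.1 should drop the counted rate for one derived from a continuous model. The documents do not support that:
- The rate is itself the question, and Aim 1 already tests walking speed on its full scale for the same comparison.
- The apparent gain depends on how the AR(1) value is read. With 20 per group and 0.45 taken as the baseline-to-post correlation, the SD of change is 0.35 × √(2 × 0.55) = 0.367 and a comparison of means has about 39% power. With one intermediate occasion the correlation is 0.45² = 0.20, the SD 0.442 and the power 29%. Over 12 occasions the correlation is near 0, the SD 0.495 and the power 24%.
- A modelled rate relies on a distribution. Section 11.0 reports that pilot walking speed needed a log transformation, and a fixed threshold in m/s is not a single cut on that scale. If benefit really comes as a mixture of responders and non-responders, a simulation under assumed gains put the modelled difference 3 to 8 points too low, while the count was unbiased.

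**Conclusion.** The point holds for Hypothesis 3.2, as a cheap improvement rather than a flaw that undermines the trial. On the fair reading of Aim 3, predictors would be sought for a yes/no response within strata of 30, although continuous or ordinal outcomes are collected. With one normal predictor, r of 0.3 to 0.6, 30% to 50% responding and a two-sided 5% test, the loss is about 12 to 27 percentage points. Across the wider inputs tried it is about 5 to 35. The direction was the same in every case; the size rests on assumptions that the plan neither states nor contradicts. The point does not extend to Hypothesis 3.1, where replacing the count with a modelled rate is a trade-off and not a clear gain.

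**What to change.** In the statistical approach text of section 11.0:
- State that the main Hypothesis 3.2 analysis uses a continuous outcome, for example post-training self-selected walking speed adjusted for baseline speed and training arm. Model it on the candidate predictors within each Pp stratum, or in one model with predictor-by-stratum interactions.
- Report responder/non-responder classification as supportive, using a stated definition of response.
- Keep the counted response rate as the analysis for Hypothesis 3.1.

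The cost is SAP wording and a little more analysis; no new data, visits or participants are needed. The downside is that predictors are then expressed for size of gain, so a responder summary must be shown beside them for clinical use.
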